**8.3.4 Visit 4: Follow-up Avaira Vitality (After 2 weeks of wear)**

The 2-week follow-up visit for pair 2 will be scheduled two weeks (**14 + 2 days**) from the initial lens dispensing date for pair 2. The subject should wear the lenses for a minimum of 2 hours

prior to the appointment. If the subject attends without lenses or with less than 2 hours of lens wear on that day and they are not having any problems with their lenses, the visit should be rescheduled, if possible within the visit window. The same variables as those collected on section 8.3.3 (visit 3a) will be assessed at this visit.

### 8.3.5 Visit 5: Follow-up Avaira Vitality (After 4 weeks of wear / exit)

The 4-week follow-up visit for pair 2 will be scheduled four weeks (28 + 2 days) from the initial lens dispensing date for pair 2. The subject should wear the lenses for a minimum of 2 hours prior to the appointment. If the subject attends without lenses or with less than 2 hours of lens wear on that day and they are not having any problems with their lenses, the visit should be rescheduled, if possible within the visit window. The same variables as those collected on section 8.3.3 (visit 3a) will be assessed at this visit. In addition, a lens preference question between habitual, (Clariti Elite Asphere), and test lenses, (Avaira Vitality sphere), will be asked at the end of this visit.

- The Study Exit Form must be completed when a subject exits the study. This will occur either at study completion, i.e. at Visit 5, or if the subject is discontinued from the study at another time. If there are records entered into the clinics own patient chart system the exit date should be recorded on these source documents. A Study Exit Form must be completed for all subjects who have taken a study ID number. Post-study follow-up visits will be scheduled if the Investigator judges this is necessary.
- [REDACTED]
  - [REDACTED]
  - [REDACTED]
  - [REDACTED]
  - [REDACTED]
  - Post-study follow-up requirement (Y/N). If yes, the reason and date of the follow-visit must also be recorded.
- If the subject is being exited due to discontinuation, further details need to be recorded on the exit form.

## 9 Adverse Event Reporting

### 9.1 Adverse Response Definitions

**Adverse Event (AE):** An AE refers to any untoward medical occurrence (sign, symptom or disease) in a trial subject that does not necessarily have a causal relationship with the study device. AEs may be classified as ‘unanticipated adverse device effects,’ ‘serious AEs,’ ‘significant AEs,’ or ‘non-significant AEs,’ as defined below. AE classification, coding (for reporting to the sponsor) and examples are provided in the following table of Contact Lens Adverse Event Classification and Reporting:

Classification	Definition
Serious Adverse Event	Those events that are life-threatening, or result in permanent impairment of a body function, or permanent damage to a body structure or necessitate medical (therapeutic) or surgical intervention to preclude permanent impairment of a body function or permanent damage to a body structure.
Unanticipated Adverse Device Effect	Adverse events in a clinical trial that were not previously identified in the protocol in terms of nature, severity, or degree of incidence. An Unanticipated Serious Adverse Device Effect is an unanticipated adverse event that is serious in nature and caused by or associated with the device and is considered reportable.
Significant Adverse Event	Those non-serious adverse events that occur with contact lens usage that are not sight-threatening but are usually symptomatic and may warrant therapeutic management and /or temporary or permanent discontinuation of contact lens wear.
Non-Significant Adverse Events	Those less severe non-serious adverse events that occur with contact lens usage that are not sight-threatening, may or may not be symptomatic and may warrant palliative management, such as ocular lubricants or temporary interruption of contact lens wear.

Code	Condition	Potential AE Classification	Reporting
01	Presumed infectious corneal ulcer	SERIOUS	Notify sponsor as soon as possible, within 24 hrs; IRB reporting as per requirements
02	Permanent loss of $\geq 2$ lines of best spectacle corrected visual acuity (BSCVA)	SERIOUS	
03	Corneal injury that results in permanent opacification within central cornea (6mm)	SERIOUS	
04	Neovascularization within the central 6mm of cornea	SERIOUS	
05	Uveitis or Iritis	SERIOUS	

06	Endophthalmitis	SERIOUS	
07	Hyphema	SERIOUS	
08	Hypopyon	SERIOUS	
09	Persistent epithelial defect	SERIOUS	
00	Other serious event	SERIOUS	
11	Peripheral non-infectious ulcer (outside central 6mm)	SIGNIFICANT	Notify sponsor as soon as possible, within 5 working days; IRB reporting as per requirements
12	Symptomatic corneal infiltrative events	SIGNIFICANT	
13	Superior epithelial arcuate lesions (SEALs) involving epithelial split	SIGNIFICANT	
14	Any temporary loss of $\geq 2$ lines BSCVA for $\geq 2$ wks	SIGNIFICANT	
15	Corneal staining $\geq$ dense coalescent staining up to 2mm in diameter (i.e. moderate staining)	SIGNIFICANT	
16	Corneal neovascularization $\geq$ 1.0mm to 1.5mm vessel penetration (if 2 Grade change from baseline)	SIGNIFICANT	
17	Any sign and/or symptom for which subject is administered therapeutic treatment or which necessitates discontinuation of lens wear for $\geq 2$ weeks	SIGNIFICANT	
10	Other significant event	SIGNIFICANT	
21	Conjunctivitis: bacterial, viral, allergic	NON-SIGNIFICANT	
22	Papillary conjunctivitis if $\geq$ mild scattered papillae/follicles approximately 1mm in diameter (if 2 Grade change from baseline)	NON-SIGNIFICANT	
25	Asymptomatic corneal infiltrative events	NON-SIGNIFICANT	
26	Localized allergic reaction	NON-SIGNIFICANT	
27	Contact dermatitis	NON-SIGNIFICANT	
28	Any sign and/or symptom for which temporary lens discontinuation for $> 1$ day is recommended	NON-SIGNIFICANT	
20	Other non-significant sign and/or symptom	NON-SIGNIFICANT	

### Normal or adaptive symptoms

Transient symptoms such as end-of-day dryness, lens awareness, itching or burning or other discomfort may occur with contact lens wear and may occasionally reduce wearing time. ***These are not reported as adverse events unless they are unexpected in nature, severity or rate of occurrence.***

## 9.2 Procedures for Adverse Events

---

Treatment of an adverse event will depend on its nature and severity. Based on the clinical judgment of the investigator the subject may be referred to an ophthalmologist for treatment. The investigator will attempt to determine whether the reaction is related to the test device or a result of other factors.

An Adverse Event Form will be completed for each adverse event. If both eyes are involved, a separate Adverse Event Form will be completed for each eye. Whenever possible, the adverse event will be photo-documented.

Expenses incurred for medical treatment as part of study participation will be paid by the sponsor (bills and prescription receipts kept). The subject must be followed until resolution and a written report completed indicating the subsequent treatment and resolution of the condition.

## 9.3 Discontinuation from the Study

---

All discontinuations will be fully documented on the appropriate CRF Exit and Adverse Event forms as needed. Participants will be followed until resolution (in most instances) and are free of the ophthalmic insert related complications or other ocular pathology. When possible study lenses involved in an Adverse Event will be returned to the sponsor in a new tightly sealed contact lens case, and labeled with the subject identification and stored in Unisol non-preserved saline.

## 9.4 Reporting Adverse Events

---

All potential **Serious and Unanticipated Adverse Device Effects** that are related or possibly related to subject participation in the investigation will be reported to the Principal Investigator and the sponsor within 24 hours of the investigator becoming aware of the event. The Principal Investigator will report the event to the EC/IRB as soon as possible (by fax, mail/delivery, phone, or email), but within 10 business days of becoming aware of the problem. *All fatal or life threatening events will be reported immediately to the IRB.*

**Significant and Non-Significant Adverse Events** will be reported to the sponsor as soon as possible, but no later than 5 working days after the occurrence. [REDACTED]

[REDACTED]  
[REDACTED]  
[REDACTED]

[REDACTED]  
[REDACTED]  
[REDACTED]

## 10 Statistical Analysis and Sample Size

[figure not shown]
### 10.1 Statistical analysis

Summary statistics will be produced (e.g. mean, standard deviation). Differences between lenses will be compared using Paired t-tests. Paired t-tests / analysis of variance for normal (interval/continuous) data, Wilcoxon's signed ranks test for non-normal (ordinal) data, chi-squares test for nominal data. A binomial test will be used to evaluate lens preference questions. All participants who are evaluated will be used in the analysis. In the event of missing data, individual data points will be excluded in the analysis and not extrapolated from the collected data.

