### 3.1 Study Hypothesis

---

- Null hypothesis ( $H_0$ ): There is no difference in lens performance between the study lenses for the key variables tested.
- Alternative hypothesis ( $H_1$ ): There is a difference in lens performance between the study lenses for the key variables tested.

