## 4 Study Design

---

This is a prospective, subject masked; bilateral, 4-week refit study comparing the fitting characteristics of Clariti Elite sphere lenses, (somofilcon A), against Avaira Vitality silicone hydrogel sphere lenses (fanfilcon A). A total of 40 subjects will be enrolled with the aim of completing 34.

Subject's will be evaluated at the first visit and then fitted with both study lenses to confirm lens fit and optimize visual acuity if needed. At the second visit, the first pair of study lenses, (e.g. somofilcon A), will be dispensed and worn for 4-weeks. After 4-weeks of daily wear with the first pair, subjects will return for a third evaluation and then fitted with the second pair, (e.g. fanfilcon A), of study lenses for 4-weeks. A fourth visit will be scheduled after 2-weeks of lens wear. A fifth and final visit will be scheduled after 4-week of lens wear. The study timeline is shown in Appendix 2.

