### 8.2.6 Masking and Control of Study Materials

The study contact lenses will be **masked to the subject only**. Study lenses will be transferred, by an assistant, out of their packaging to unmarked new contact lens cases filled with unpreserved sterile saline just prior to dispensing to maintain subject masking of the study lenses.

- [REDACTED]
  - [REDACTED]
    - [REDACTED]
    - [REDACTED]
  - [REDACTED]
    - [REDACTED]
    - [REDACTED]
- Lens Fit
  - Lens centration (centered/slightly decentered/substantially decentered)
  - Corneal coverage [Y/N]
  - Post-blink movement (0 - 5 Likert scale)
  - Lens tightness. Push up test (0% to 100%, 50% optimum)
  - Overall fit acceptance (0 - 4) and reason if Grade 2 or less.
  - Remove study lenses and perform slit lamp examination
- [REDACTED]
  - [REDACTED]
    - [REDACTED]
    - [REDACTED]
    - [REDACTED]
    - [REDACTED]
    - [REDACTED]
  - [REDACTED]
    - [REDACTED]
    - [REDACTED]
    - [REDACTED]
    - [REDACTED]

Visit 3b: Dispense Avaira Vitality Lenses

The study subjects will undergo a trial fit in each eye with the second pair of study lenses.

- The performance of the second pair of study lenses should be assessed after 10 - 15 minutes settling time. The same variables as those collected on *visit 2, section 8.3.2* will be assessed.

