### 10.2 Sample size

A sample size was calculated using data from a previous study. Assuming a standard deviation of 1.9 points, with 84% power and an alpha level of 0.05, a sample size of 34 subjects is required to detect a difference of 1.0 points, (0-10 scale), between lenses [REDACTED] 40 subjects will be enrolled to account for potential drops outs or discontinuations.

Figure 1. Sample size calculation (Minitab 16 Statistics software)

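### Section 10.1 gives no rule for handling two eyes per subject in the lens-fit tests, and its chi-square test also ignores that the same subjects wear both lenses

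*Combined protocol and SAP*

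**What the plan says.** Section 4 describes the design: "This is a prospective, subject masked; bilateral, 4-week refit study". Section 2 gives lens fitting characteristics as the primary variable. The Visit 3 procedures list the items: centration in three categories, corneal coverage as yes or no, post-blink movement on a 0-5 scale, push-up tightness from 0 to 100%, and overall acceptance from 0 to 4. The Visit 3b instructions place the fitting at the level of the eye: "The study subjects will undergo a trial fit in each eye with the second pair of study lenses".

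Section 10.1 states "Differences between lenses will be compared using Paired t-tests". It then assigns paired t-tests or analysis of variance to normally distributed data, Wilcoxon signed ranks to ordinal data and chi-square to nominal data. It includes every evaluated participant and leaves missing points out rather than filling them in. It does not mention the eye.

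Section 10.2 counts people: "a sample size of 34 subjects is required". That calculation uses a 0-10 scale.

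**The concern.** Each fit item is a property of one lens on one eye, so the natural data set has two records per subject per lens. The paired t and signed-ranks tests need independent pairs, and the two eyes of one person are not independent. If both eyes went in as separate pairs, the standard error would be too small and a difference between lenses would be declared too often. This would affect the primary variable.

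The chi-square test raises a second problem. Every subject wears both lenses, so the two sets of yes/no or category results are matched. An ordinary chi-square treats them as two unrelated samples. That is wrong even with one value per subject, and two eyes add clustering on top.

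Leaving the unit open also means that an eye-level or a subject-level result could be chosen after the data are seen.

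**Working it through.** **1. The plan's own figure.** Inputs from section 10.2: SD 1.9, difference 1.0, alpha 0.05, n = 34, power 84%. The test is taken as two-sided because section 3.1 states the alternative as "There is a difference in lens performance between the study lenses for the key variables tested". The SD is read as that of the within-subject difference.

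- Noncentrality = (1.0/1.9) × √34 = 3.07, with 33 degrees of freedom.
- Power from the noncentral t = 84.6%, which agrees with 84%. With n = 33 it is 83.4%.
- A two-sample reading with 34 per group gives 58%, which does not agree.
- Dropout: 34/(1 − 0.15) = 40, which matches enrolment.

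The sizing is therefore a paired t-test with one difference per subject. No readable fit item uses a 0-10 scale, so the calculation does not show how the fit items would be reduced to one value per subject.

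**2. Paired t and Wilcoxon with eyes pooled.** Let ρ be the correlation between a subject's two eyes in the lens-to-lens difference. The documents give no value, so ρ is an assumption. With n subjects and 2n eye-level differences of variance σ²:

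- variance assumed by the test = σ²/(2n)
- true variance of the mean = (σ²/(2n)) × (1 + ρ)
- actual two-sided type I error = 2 × [1 − Φ(1.96/√(1 + ρ))]

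For example, at ρ = 0.5: 1.96/√1.5 = 1.600, which gives 11.0%.

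| Assumed ρ | Formula | Paired t, simulated (34 subjects, 68 pairs) | Wilcoxon, simulated (34 subjects, 68 pairs) |
|---|---|---|---|
| 0 | 5.0% | 5.0% | not run |
| 0.3 | 8.6% | 8.5% | 8.8% |
| 0.5 | 11.0% | 11.1% | 10.7% |
| 0.8 | 14.4% | 14.6% | not run |
| 0.9 | 15.5% | 15.9% | 15.5% |
| 1.0 | 16.6% | 17.0% | not run |

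The simulations used normally distributed differences, with 100,000 runs per value for the t-test and 4,000 for Wilcoxon. Using 40 subjects instead of 34 gives nearly the same t-test results.

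**3. Paired t with one value per subject.** When the two eyes are averaged first, simulated type I error is 4.9-5.1% at every ρ from 0 to 1, for 34 or 40 subjects.

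**4. Chi-square for nominal items.** These figures are for a yes/no item in 34 subjects and rest on assumed correlations.

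- One value per subject: between-lens correlations of 0.3-0.5 (on an underlying normal scale) give about 1.6-3.5%. Ignoring the lens pairing makes the test conservative.
- Both eyes pooled: the two faults pull in opposite directions. The correlations are, in order, same eye across lenses / same lens across eyes / across both.
  - 0.5/0.5/0.3 gives 2.8-3.4%.
  - 0.5/0.7/0.4 gives 3.8-4.6%.
  - 0.3/0.5/0.2 gives 5.0-5.3%.
  - 0/0.5/0 (no correlation between lenses) gives 8.5-8.7%.

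The chi-square error can therefore lie on either side of 5%.

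**The case against.** The strongest reply is that nothing in the plan says eyes will be pooled. Participants and subjects are the only units named in sections 10.1 and 10.2, and the sample size reproduces only with one difference per subject. With one value per subject, the paired t-test holds its 5%. This stands, and it is why the 9-16% is conditional. It does not close the gap, because the readable text has no rule for getting from two eyes to one value.

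A reader might infer that 68 eye records will enter the tests and that the type I error is therefore inflated. The documents do not support that. The missing-data sentence does not help, because it only rules out imputation and fits subject-level data equally well.

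Other points that stand:

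- Analysis of variance is also named, and it could carry subject and eye as factors, but no such model is specified.
- Most fit items are ordinal or nominal, so section 10.1 sends them to Wilcoxon or chi-square and not to the t-test. Wilcoxon shows the same inflation when eyes are pooled. For chi-square, inflation is not established.
- Subject effects common to both lenses cancel in the difference. High inter-eye correlation of the raw grades would not by itself justify a ρ of 0.8-0.9.
- Parts of the visit procedures and the appendices are missing or redacted, so an eye-level rule could be there. Section 10.1 does not refer to one.

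**Conclusion.** The point holds as a gap in specification, together with one unsuitable test. Section 10.1 neither names the unit of analysis nor handles two eyes, in a bilateral study whose readable primary variable is measured per eye. If eyes were entered as independent pairs in the paired t or Wilcoxon test, two-sided type I error would be about 9-16% for an assumed ρ of 0.3-0.9, and 5-17% over the whole range 0-1.

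Chi-square for coverage, and for centration if treated as nominal, does not suit matched data whichever unit is used. Its error rate is wrong and possibly conservative, with the direction depending on correlations that the documents do not give.

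It would be tempting to conclude that the 34-subject figure is also wrong. It is not: it reproduces as a subject-level calculation and is unaffected. This is a cheap improvement.

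**What to change.** In section 10.1:

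- State that the subject is the unit of analysis.
- For movement, tightness and overall acceptance, average the two eyes per subject and lens, then apply the paired t or Wilcoxon test to the subject-level values.
- For coverage, and for centration if treated as nominal, replace chi-square with a method that respects both the lens pairing and the two eyes, for example GEE or a mixed model clustered on subject. State whether centration is nominal or ordinal.

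Scoring each subject by the worse eye is not recommended as the default, because it changes the quantity being estimated.

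The cost is a few sentences and slightly more programming. No extra subjects or data are needed, and the target of 34 completers stands. Standard errors will be wider than pooled eyes would give when ρ is positive, and they will be correct.

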**The primary variables of interest are:**

- Lens fitting characteristics

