### 8.2.1 Contact lens

All subjects will be trial fitted and, if suitable, dispensed the clariti® elite sphere and Avaira Vitality™ sphere lenses. The study lenses and solutions will be provided by the Sponsor. Details of the contact lenses are shown in Table 1.

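### Section 10.1 gives nominal data an unqualified chi-square, although corneal coverage (yes/no) is recorded on the same subjects with both lenses; name McNemar's test on one record per subject (minor)

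*Combined protocol and SAP*

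**What the plan says.** Section 10.1 opens with a general rule, "Differences between lenses will be compared using Paired t-tests", and then assigns tests by data type: "Paired t-tests / analysis of variance for normal (interval/continuous) data, Wilcoxon's signed ranks test for non-normal (ordinal) data", followed by "chi-squares test for nominal data". Lens preference is handled separately, by a binomial test. Apart from the analysis-of-variance alternative, the continuous and ordinal tests named are within-subject tests. The nominal test carries no paired qualifier.

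The item affected is "Corneal coverage [Y/N", recorded yes or no. It stands in the Lens Fit list just before Visit 3b. By the table of contents that is section 8.3.3, although in the supplied text it follows section 8.2.6. Section 2 gives "Lens fitting characteristics" as the primary variables, so coverage is a primary-class item. On who wears what, section 8.2.1 says "All subjects will be trial fitted and, if suitable, dispensed the" two study lenses. For Visit 5, with Avaira Vitality, section 8.3.5 says "The same variables as those collected on section 8.3.3 (visit 3a) will be assessed at this visit", and section 8.3.4 says the same for Visit 4.

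Section 10.2 counts subjects: "a sample size of 34 subjects is required to detect a difference of 1.0 points". Section 4 calls the study bilateral. The visible text of 10.1 says neither whether the record is the eye or the subject, nor which Avaira Vitality visit is compared with Visit 3a.

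**The concern.** Each subject supplies a coverage result with Clariti Elite and another with Avaira Vitality. The two are likely to be positively correlated, because the same eyes wear both lenses. The ordinary (Pearson) chi-square on a lens-by-outcome table assumes independent records. It therefore overstates the variance of the difference and rejects too rarely.

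An analyst who followed 10.1 to the letter could miss a real difference between lenses in a primary-class item. The silence on eye or subject adds a second risk, in the other direction. If both eyes enter as separate pairs, even a paired test can reject too often.

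**Working it through.** **The plan's own figure.** Section 10.2 gives SD 1.9, difference 1.0, alpha 0.05, 34 subjects and 84% power. A two-sided paired t-test with one value per subject has noncentrality √34 × 1.0/1.9 = 3.07 on 33 degrees of freedom, and power 84.6%. It gives 83.4% at n = 33, so 34 is the smallest n that reaches 84%. A two-sample reading would need 64 per group. The stated size reproduces, and it does so as a within-subject comparison counted in subjects.

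**Direction of the error.** Let p be the common coverage rate and ρ the within-subject correlation. The variance of the difference in proportions is 2p(1−p)(1−ρ)/n, but Pearson uses 2p(1−p)/n. Its z statistic is thus shrunk by √(1−ρ). At ρ = 0.3 the factor is 0.837, so the effective critical value is 1.96/0.837 = 2.34 and the approximate real error is 1.9%.

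**Exact enumeration.** Inputs: n = 34 (section 10.2), two-sided 0.05, one record per subject. Coverage rates p1 and p2 and correlation ρ are assumptions, because the documents give none. The cells of the paired table are p11 = p1·p2 + ρ√[p1(1−p1)p2(1−p2)], p10 = p1 − p11, p01 = p2 − p11, and the remainder. For 80% v 60% at ρ = 0.3: p11 = 0.48 + 0.3 × 0.196 = 0.539, p10 = 0.261, p01 = 0.061, p00 = 0.139.

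With b and c the two discordant counts, x and y the numbers covered with each lens, and t = x + y:

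- Pearson: 2n(x − y)²/[t(2n − t)]
- McNemar, uncorrected: (b − c)²/(b + c)

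Real error when the lenses do not differ:

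| Coverage | ρ | Pearson | McNemar | Mid-p McNemar |
|---|---|---|---|---|
| 60% v 60% | 0 | 5.3% | 4.9% | 4.7% |
| 60% v 60% | 0.3 | 2.1% | 4.3% | 4.3% |
| 80% v 80% | 0 | 5.3% | 4.3% | 4.2% |
| 80% v 80% | 0.3 | 2.2% | 4.5% | 3.8% |
| 90% v 90% | 0.3 | 2.4% | 4.5% | 1.9% |
| 95% v 95% | 0.3 | 1.2% | 1.8% | 0.4% |

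The highest value for uncorrected McNemar among the scenarios checked was 5.03% (50% v 50%, ρ = 0).

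Power:

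| Coverage | ρ | Pearson | McNemar | Mid-p McNemar |
|---|---|---|---|---|
| 80% v 60% | 0 | 46% | 42% | 42% |
| 80% v 60% | 0.1 | 45% | 45% | 45% |
| 80% v 60% | 0.3 | 45% | 54% | 54% |
| 90% v 70% | 0 | 57% | 52% | 52% |
| 90% v 70% | 0.3 | 58% | 68% | 67% |
| 95% v 85% | 0.3 | 26% | 35% | 24% |
| 97% v 90% | 0.3 | 16% | 21% | 10% |
| 98% v 92% | 0.3 | 12% | 15% | 6% |

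At high coverage uncorrected McNemar stays ahead of Pearson, but mid-p falls behind it. Mid-p cannot reach 0.05 with fewer than 5 discordant pairs, and the chance of that is 79% at 97% v 90% with ρ = 0.3.

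**Illustration (invented table).** Take 20 covered with both lenses, 8 with one only, 1 with the other only and 5 with neither, so x = 28, y = 21, t = 49. Pearson: 68 × 49/(49 × 19) = 3.58, p = 0.059. McNemar: 49/9 = 5.44, p = 0.020. The smallest expected count is 19/2 = 9.5, so sparse cells do not explain the gap.

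**Eyes as records.** In a simulation of 34 subjects with two eyes each at 80% coverage, treating the 68 eyes as independent pairs gave McNemar a real error of about 8% to 13% when the response to a lens was shared between eyes, and 5.0% when it was not.

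**The case against.** The strongest reply is that 10.1 already means a paired analysis. It opens with paired tests for differences between lenses, and McNemar's test is itself of chi-square type. This largely stands. A reader might infer that the sponsor plans an unpaired analysis or that the design is wrong, and the documents do not support that. What remains is that the test is not named, and an ordinary chi-square would satisfy the wording.

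The second reply is that the effect is small. Coverage is the only clearly nominal item among the visible lens-fit items, the sample size rests on a 0–10 score, and lenses are dispensed only if suitable, so coverage may be near 100%. This also stands. A reader might infer a large power loss by assuming a correlation of 0.5. But at 90% v 70% the largest possible correlation is 0.509, so 0.5 leaves only 0.1% of subjects covered with the worse lens alone. Such figures should not carry the point. Nor does an ordinary chi-square with one record per subject create false claims of a difference to any important extent: its error is below 5% under positive correlation and about 5% to 6% at zero.

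The third reply is that parts of section 8.3 are redacted or not supplied, so a rule for two eyes may exist there. That cannot be ruled out, and the fix allows for it. The test sentence in 10.1 is legible.

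**Conclusion.** The point holds as a minor correction to the named test. Coverage is paired, and an ordinary chi-square ignores the pairing. At an assumed correlation of 0.3 its real error is about 2%, and it gives up about 10 points of power at 80% v 60% or 90% v 70%, and about 5 points at 97% v 90%. At a correlation of about 0.1 the tests are level at 80% v 60%. At zero McNemar is about 3 to 5 points behind (46% v 42%; 57% v 52%). All of this assumes 34 subjects, one record each, and rates and correlations that the documents do not supply. The sample size of 34 is not in question, and the preference test is unaffected.

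**What to change.** In section 10.1, replace "chi-squares test for nominal data" with wording such as:

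> Binary items compared between lenses: McNemar's test without continuity correction, on one record per subject (for example, covered only if yes in both eyes, unless section 8.3 already sets an eye rule), Visit 3a against Visit 5. Any analysis that uses both eyes accounts for clustering within subject.

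This visit pair compares 4 weeks of wear with each lens. Mid-p McNemar can be reported as a sensitivity analysis. That is useful when discordant pairs are few: with 4 pairs all one way the uncorrected statistic is 4²/4 = 4.0, just above 3.84, while mid-p is (1/2)⁴ = 0.0625. It should not be the main test, because it loses power at high coverage.

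The cost is two sentences, with no new data, subjects or procedures. The downsides are a small loss of power if the within-subject correlation is near zero, some eye-level information given up by a both-eyes rule, and little practical effect if coverage is near 100%.
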